9.2.1.2 Index Date

Depending on the date of first evidence of AF over the study period, AF patients will be included at the following dates:

- On 1st January 2016 for **prevalent AF patients** (i.e., patients diagnosed AF during the historical period);
- On the first date of evidence of AF (first date of diagnosis of AF identified either by a LTD or the start date of a hospitalization, or the first date of OAC dispensation) for **incident AF patients**.

A patient will be considered exposed to OAC at the time of his/her inclusion if at least one dispensation of OAC is issued within 30 days after inclusion (including date of inclusion). In such a case, the index date will be the date of the first dispensation of OAC (cf. Appendix 1).

Otherwise, if no dispensation of OAC will be identified within 30 days from inclusion, the index date will be the date of inclusion.

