Unclassified patients	
Binary variable (Yes/No)
 
Equals to "Yes" if Confirmed AF = "No" and Confirmed DVT/PE = "No"
 
The algorithm will be applied on the unclassified patients. Patients with both confirmed AF and DVT/PE will be excluded.
 
Equals to "No" in other cases

Then, a logistic model included 14 independent covariables will be applied on unclassified patients to identify AF outpatients initiating OAC ([Table III](#)).

Table III. Derived variable for the selection of the population – Covariables included in the logistic model

Variable	Definition
Age	
Categorical variable (<65 years old / 65-74 / 75-79 / ≥80 years old)
 
Derived based on the date of birth attributed to the patient after cleaning the data extraction
 
Equals to:
 
 9. "<65 years old" if the absolute difference between the year of index date and the year of birth is strictly lower than 65 years old 10. "65-74" if the absolute difference between the year of index date and the year of birth is between 65 and 74 years old 11. "75-79" if the absolute difference between the year of index date and the year of birth is between 75 and 79 years old 12. "≥80 years old" if the absolute difference between the year of index date and the year of birth is upper than 80 years old 
See also Data Management Plan in section Error! Reference source not found.

Gender	Binary variable (Female / Male) Equals to the value attributed to the patient after cleaning the data extraction See Data Management Plan in section Error! Reference source not found.
Cardiologist prescriber	Binary variable (Yes / No) Equals to "Yes" if the prescriber of the initiation of the OAC is a cardiologist Code CNAM repository (variable PSE_SPE_COD): 03 Equals to "No" in other cases
Initiation of beta-blockers	Binary variable (Yes / No) Equals to "Yes" if the patient has reimbursements for at least one dispensation at pharmacy of any beta-blockers during the 6 weeks preceding the first date of OAC delivery and with no filled prescription for the medication during the previous 180 days ATC codes: C07xxxx Equals to "No" in other cases
Use of beta-blockers	Binary variable (Yes / No) Equals to "Yes" if the patient has reimbursements for at least one dispensation at pharmacy of any beta-blockers during the 6 weeks preceding the first date of OAC delivery ATC codes: C07xxxx Equals to "No" in other cases

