Risk of falls	
Binary variable (Yes / No)
 
Patients at risk of falls identified by an algorithm adapted to SNDS data (22)
 
ICD-10 codes:
 
 • Fractures: S12xxx, S22xxx, S32xxx, S42xxx, S52xxx, S62xxx, S72xxx, S82xxx, T02xx, T08xx, T12xx, T13xx (including open

	
and closed fractures, 5th digit = 0 : closed fracture, 5th digit = 1 : open fracture)
 
 • Parkinson disease, and other extrapyramidal and movement disorders: G20-G26 (G22*, G26* excluded) • Demyelinating diseases of the central nervous system, ataxias: G35-G37, G11, R26, R27 
ATC codes: C02A (Centrally acting antihypertensives), N05A (N05AN excluded) (antipsychotics), N05B (anxiolytics), N06AX21, N06AA09, N06AA12, N06AX03, N06AX11, N06AA05 (sedative antidepressants), R06AD01, R06AB01, R06AB51, R06AA08, R06AB02, R06AB52, R06AA09, R06AA59, N05BB01, N05BB51, R06AX17, R06AE05, R06AD07, R06AX25, R06AE06, R06AD08, R06AD02, R06AD52, R06AX28 (sedative antihistamines), N05CD (benzodiazepines), N05CF (Z-drugs)

Frail patients	
Binary variable (Yes / No)
 
See Table VTable I

Morbid obesity	
Binary variable (Yes / No)
 
Equals to "Yes" if the patient is hospitalized with any discharge diagnosis (i.e., main or related diagnosis) of obesity on or in the 2 years prior to the index date
 
ICD-10 codes: E66.x
 
Equals to "No" in other cases

History of major bleeding	
Binary variable (Yes / No)
 
Equals to "Yes" if the patient is hospitalized with any discharge diagnosis (i.e., main or related diagnosis) of major bleeding on or in the 2 years prior to the index date
 
ICD-10 codes: I60.x, I61.x, I62.9, S06.4, S06.5, S06.6, I85.0, K22.6, K25.0, K25.2, K25.4, K25.6, K26.0, K26.2, K26.4, K26.6, K27.0, K27.2, K27.4, K27.6, K28.0, K28.2, K28.4, K28.6, K29.0, K62.5, K92.0, K92.1, K92.2, D62, H35.6, H43.1 H45.0, H92.2, I31.2, J94.2, R04.x, K66.1, M25.0, N02, N93.8, N93.9, N95.0, R31, R58, T79.2
 
Equals to "No" in other cases

At least one visit to a nursing home	
Binary variable (Yes / No)
 
Equals to "Yes" if the patient has at least one reimbursement corresponding to a nursing home on or in the 2 years prior to the index date

History of dementia	
Binary variable (Yes / No)

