9.4.3.2 Comparison of the incidence of stroke, major bleeding, death

The incidence rate ratio for each event of interest (stroke, major bleeding and death; see [Table VIII](#) for derivation of events of interest) will be compared using a Cox regression model with OAC exposure (see [Table VII](#) for derivation of exposure sequences) considered as time-dependent variable adjusted for covariates. Covariates will be derived at index date as indicated in [Table XV](#).

Table XV. Derived variables for confounders

Variable	Definition
Age	Categorical variable (<80 years old / 80–90 / >90 years old) See Table III
Sex	Binary variable (Female / Male) See Table III
Prescriber's specialty at initiation of OAC	Categorical variable (Hospital-based physician/ City cardiologist/ Generalist practitioners/Other) See Table III
Having Malnutrition	Binary variable (Yes / No) See Table III
Risk of falls	Binary variable (Yes / No) See Table III
Frail patients	Binary variable (Yes / No) See Table V
Morbid obesity	Binary variable (Yes / No) See Table VI
At least one visit to a nursing home	Binary variable (Yes / No) See Table VI
Concomitant treatments	Binary variable (Yes / No) for each concomitant treatment listed in Table XIV

For example, for antiplatelet drugs, equals to “Yes” if the patient has at least one reimbursement for an antiplatelet drug in the 4 months before the index date
	
HAS-BLED score	Categorical variable (0, 1, 2, 3, ≥ 4) See Table VI
CHAD₂DS₂VASC score	Categorical variable (0, 1, 2, 3, 4, ≥ 5) See Table VI
Age adjusted Charlson Cormordity Index (ACCI) adapted to SNDS data	Categorical variable (0, 1-2, 3-4, ≥ 5) See Table VI XII

9.4.3.3 *Estimation of the AF annual standardized incidence rate and prevalence*

All the variables in [Table XVI](#) will be derived for all AF patients in France in 2016, 2017, 2018 and 2019.

Table XVI. Derived variables for incidence and prevalence

Variable	Definition
Incident AF patient	Binary variable (Yes / No) See Table X
Prevalent AF patient	Binary variable (Yes / No) Equals to “Yes” if the patient is diagnosed AF during the historical period Patients belonging to the study population

9.4.3.4 *To describe the use of oral anticoagulants (OACs) in AF patients initiating treatment (AF patients exposed to OAC therapy)*

Table XVII. Derived variables for OAC treatment pattern

Variable	Definition

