Prescriber's specialty	Categorical variable (Hospital-based physician/ City cardiologist/ Generalist practitioners/Other) Equal to 'Hospital-based physician' if PSE_STJ_COD = 61, 62 Equal to 'City cardiologist' if the variable PSE_SPE_COD (medical specialty of the prescriber) = 3 and PSE_STJ_COD = 51, 55, 63, 64, 69. Equal to 'Generalist practitioners' if the variable PSE_SPE_COD = 1 and PSE_STJ_COD = 51, 55, 63, 64, 69. Equal to 'Other' if the variable PSE_SPE_COD not in 3 or 1.
-------------------------------	---

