9.7.4.2 Comparison of the incidence of stroke, major bleeding, death

Analyses will be performed independently for each event of interest stroke, major bleeding and death.

Survival analysis will be performed to compare incidence rate (stroke, major bleeding or death) in AF incident patients exposed and unexposed to OAC therapy **excluding those with a reported outcomes of interest up to 30 days prior index date**, using a Cox regression model. The Cox regressions models will consider the first event of interest occurring in AF incident patients exposed and unexposed to OAC. OAC exposure will be considered as time-dependent variable and the models will be adjusted for covariates defined below. By applying the OAC exposure variable as a time dependent variable, estimates of Hazard Ratio will account for switches and discontinuations. Time-dependent exposure Cox proportional hazards models will be used to estimate:

- The Crude hazard ratio (i.e. the incidence rate ratio), and therefore the risk of each outcome at any point during the follow-up since index date
- The adjusted hazard ratio on potential confounders including patient:
 - Time-fixed confounders: sex, age (<80, 80-90, >90 years old), prescriber's specialty at initiation of OAC, having malnutrition (yes/no), risk of falls (yes/no), morbid obesity (yes/no), history of stroke (yes/no), history of major bleeding (yes/no), at least one visit to a nursing home (yes/no), history of dementia (yes/no), concomitant treatments (e.g. receiving at least one antiplatelet drugs (yes/no), other anticoagulant drugs (yes/no), etc. - cf. *Table XV for all confounders*)
 - Time-dependent confounders: AOC treatment exposure

In a first model, patient exposure will be modelled according to five categories: exposure to apixaban, dabigatran or rivaroxaban, exposure to VKA or unexposed patients. In a second model, exposure to DOACs will be integrated instead of exposure to apixaban, dabigatran or rivaroxaban. For both models, the reference for comparison will be VKA exposure.

Same models will be performed on AF incident patients with a high thromboembolic risk (if modified CHAD₂DS₂VASC score is ≥ 2 for males and ≥ 3 females). Patient exposure will be modelled according to three categories: exposure to DOAC (Apixaban, Dabigatran or Rivaroxaban), exposure to VKA or unexposed patients. The reference for comparison will also be VKA exposure.

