9.7.6 Sensitivity analyses

We will perform the following sensitivity analyses:

1. Analyses on the evaluation of the incidence rate and comparison of the events of interest (stroke, major bleeding, and death) will be performed from the inclusion date for all incident AF patients (i.e. the inclusion date will be the index date for all incident patients, whether or not patients received OAC therapy within 30 days of the inclusion date).
2. Analyses including the 2020 data (given the uncertainty of the impact of the Covid 19 health crisis on the management of NVAF incident patients) will be conducted on:
 - Description of the follow-up of the study population (Table A1);
 - Sociodemographic characteristics (Tables A4 and A7), medical history and comorbidities (Table A5 and A8); concomitant treatments (Tables A6 and A9);
 - Estimation and comparisons of the incidence of interest-events in AF exposed and unexposed to OAC (primary objective - Table A2, secondary objective - Table A10);
 - Estimation of the annual incidence rate and the prevalence of AF patients (Tables A12 and A13 respectively).
3. Analyses on AF patients without the second inclusion criteria (new OAC users identified by the algorithm of *Billionnet et al.* not included) will be performed for the estimation of the annual standardized incidence and prevalence (Tables A12 and A13 respectively).
4. Analyses will be considered to test the impact of different grace periods (duration of 30 days and 90 days) in the calculation of treatment sequences for the following objectives:
 - Estimation and comparisons of the incidence of interest-events in AF exposed and unexposed to OAC (primary objective - Table A2, secondary objectives - Table A10)
5. If more than 10% of each event of interest occur during the 60 days grace period, analyses will be performed considering this event of interest in an unexposed period for the following objectives:

- Estimation and comparisons of the incidence of interest-events in AF exposed and unexposed to OAC (primary objective - Table A2, secondary objectives - Table A10)

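### The adjusted Cox models include unexposed patients but use a prescriber covariate they lack at index; the covariate lists conflict, and ACCI scores 5–9 have no category

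*SAP*

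**What the plan says.** SAP 9.7.4.2 plans time-dependent Cox models with VKA as reference. The first has five exposure categories, the second replaces the three DOACs by their class, and the high-risk models have three categories. All include unexposed. The time-fixed confounders include prescriber's "specialty at initiation of OAC, having malnutrition (yes/no), risk of falls (yes/no), morbid obesity (yes/no"), and the section refers to Table XV for the full set.

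- **Timing.** SAP 9.4.3.2: "Covariates will be derived at index date as indicated in" Table XV. SAP 9.2.1.2: "Otherwise, if no dispensation of OAC will be identified within 30 days from inclusion, the index date will be the date of inclusion".
- **Coding.** Table XV gives prescriber as "Categorical variable (Hospital-based physician/ City cardiologist/ Generalist practitioners/Other") and refers to Table III. Table III, written for the AF-selection algorithm, has a flag that is Yes "if the prescriber of the initiation of the OAC is a cardiologist" and No otherwise. Table XVII (9.4.3.4) holds the four-level rule: hospital-based is set on practice-mode codes 61 and 62, and Other applies "if the variable PSE_SPE_COD not in 3 or 1".
- **Missing data.** SAP 9.7.1 expects none and plans no imputation.
- **Sensitivity analysis 1.** SAP 9.7.6: "the inclusion date will be the index date for all incident patients, whether or not patients received OAC therapy within 30 days".
- **Shells.** The footnotes to Tables A10 and A11 give a covariate list without prescriber.
- **ACCI.** In Table VI the 3–4 group ends at 4 and the group labelled ≥5 is assigned from 10 upward.

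**The concern.** Secondary objective 3 compares patients exposed and unexposed to OAC. One adjuster does not exist at index for patients who are unexposed at index, and the SAP does not say what value they get. A programmer could lose them through missing values, pool them with another level, add a level, or omit the term, and could cite some part of the SAP for most of these choices. The adjusted model is therefore not fully pre-specified. At stake are precision, which patients and person-time inform the contrast, and agreement between the analysis text and the reported tables. Separately, the ACCI rule taken literally leaves many older patients without a category in a covariate that Table XV requires.

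**Working it through.** There is no stated figure to reproduce. The check sets the rules side by side and then uses simulations with assumed rates.

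**1. Who has a prescriber value at index** (9.2.1.2, 9.4.3.2, 9.7.6)

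| First OAC dispensing | Main analysis | Sensitivity analysis 1 |
|---|---|---|
| On inclusion date | yes | yes |
| Days 1–30 | yes (index moves to dispensing) | no (index stays at inclusion) |
| None within 30 days | no | no |

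In sensitivity analysis 1 a complete-case fit also loses the days 1–30 starters. These include patients with an event between inclusion and first dispensing, whom Table X and the shell notes say this analysis should add. If 20–60% of those starting within 30 days start on the inclusion date (assumed), then 1 − 0.60 = 40% to 1 − 0.20 = 80% of them have no value.

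**2. What each source implies for a patient unexposed at index**

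- Four levels (Tables XV and XVII): no level applies, so the value is missing and a complete-case fit drops the patient.
- Table III flag: No, pooled with patients whose prescriber is not a cardiologist.
- A10/A11 footnotes: no prescriber term.

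The four levels also overlap. A hospital physician (mode 61 or 62) whose specialty is neither 1 nor 3 meets both hospital-based and Other. The Table III reference looks unreliable: Table XV cites Table III for malnutrition and falls too, but both are defined in Table VI (for falls, "Patients at risk of falls identified by an algorithm adapted to SNDS data (22")).

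**3. Effect on the hazard ratio (HR) at index timing**

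First simulation, true HR 1 for death: 8 runs of 12,000 patients, death 0.10/year, 60% exposed at index, later initiation 0.3/year, stopping 0.2/year, follow-up 0–4 years. Unexposed versus exposed: no prescriber term 1.02, explicit level for no OAC at index 1.02, complete case 1.04.

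Second simulation, true unexposed:VKA HR 1.5: 18 scenarios of 1,200,000 patients, piecewise-exponential approximation to the Cox model. Assumed: death 10%/year on OAC, 50–75% on OAC at index, 5–40%/year start later, 20%/year stop, 0–30%/year restart, VKA 25% of OAC.

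| Assumed setting | No prescriber term | Level 'no OAC at index' |
|---|---|---|
| (a) Prescriber and index status unrelated to risk | 1.49–1.51 | 1.49–1.52 |
| (b) Prescriber related to risk and to VKA choice | 1.41–1.43 | 1.47–1.52 |
| (c) Index-unexposed carry an unmeasured relative risk of 1.5 | 1.82–2.09 | 1.49–1.51 |
| (d) Illness drives stopping | 1.60–1.73 | 1.74–1.90 |

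In (a) complete case gives 1.48–1.52. It drops the 25–50% of patients unexposed at index, with 54–85% of unexposed person-time, and multiplies the standard error of the log HR by 1.20–1.48 (explicit level: 1.07–1.23). The contrast then rests on later stops and restarts among patients exposed at index.

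**4. Covariate lists**

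| Term | 9.7.4.2 | Table XV | A10/A11 |
|---|---|---|---|
| Prescriber's specialty | yes | yes | no |
| History of stroke, major bleeding, dementia | yes | no | yes |
| Frailty, HAS-BLED, CHA2DS2-VASc, ACCI | not named | yes | no |

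**5. ACCI groups, Table VI rule applied literally**

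0 → 0; 1–2 → 1–2; 3–4 → 3–4; 5, 6, 7, 8, 9 → none; 10 or more → ≥5.

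Age gives 4 points at 80–89 and 5 at 90–99. So age 80–89 with 1–5 condition points (4 + 1 = 5 to 4 + 5 = 9) has no group. The same holds for age 90–99 with 0–4 (5 + 0 = 5 to 5 + 4 = 9).

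**The case against.** The strongest reply is that the plan fixes covariates at index date and calls prescriber time-fixed. At that timing every coding returns about the true HR when index status is unrelated to risk. That stands: the cost shown there is precision and a narrower contrast.

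Second, two of the SAP's own sources create no missing value: the Table III flag classifies everyone, and the shells omit the variable. That also stands, and it makes the defect one of inconsistent specification. No text says which source governs.

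Third, the ACCI threshold is an evident slip, since the label, Table XV and shell Tables A5 and A8 all say ≥5, and SAP 9.6 has a second statistician check the programs. The intention is indeed clear, but the derivation rule is still wrong as written.

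Fourth, 9.7.4.2 introduces its list as non-exhaustive and defers to Table XV, so its not naming the scores is no contradiction. Agreed. The real mismatches are the three histories missing from Table XV, which enter there only partly through the scores, and the shell footnotes.

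A reader might infer two stronger things. One is that the model conditions on future treatment, because of the variable's label or A11's wording that covariates are taken at or from index. With the value taken at a later first dispensing, the first simulation gave 0.59 against a true 1. But 9.4.3.2 sets derivation at index date, and the A11 list omits prescriber, so its wording cannot govern that variable.

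The other is that the unstated level by itself moves the HR a long way. The wide spread in setting (c) comes from an assumed unmeasured confounder, and the model without prescriber is the one furthest from the truth there. It is not a harm of the plan's stated timing.

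**Conclusion.** The point holds as a specification fault in a secondary analysis and should be fixed before the models are run. The textual findings are certain: a covariate that patients unexposed at index lack, no level for them, three competing sources for its coding, overlapping levels, conflicting lists, and ACCI 5–9 unassigned.

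The sizes rest on assumed rates, because the documents give none. Under them, a complete-case fit mainly costs precision (standard error 1.20–1.48 times larger) and restricts the comparison to later stops and restarts. In sensitivity analysis 1 it would also defeat the purpose of the analysis. Bias or reversal of the HR is not shown at the stated index timing. Neither omitting prescriber nor adding a level is uniformly better: the level does better in settings (b) and (c), omission in (d), and they agree in (a).

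'Every model' is true of the SAP only; the first comparison in Protocol 3.7.2.2 sets the DOACs against VKA without unexposed patients. Crude hazard ratios and the primary Table A2 rates are not affected.

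**What to change.** 1. In Table VI, assign the ≥5 group when ACCI is 5 or more.
2. Use one covariate list, measured at index date, in 9.7.4.2, Table XV and the A10/A11 footnotes.
3. For models with an unexposed category, including sensitivity analysis 1, pre-specify either no prescriber term (as the A10/A11 footnotes have it) or an explicit 'no OAC at index' level, and report the other as a sensitivity model. State that the explicit level makes the contrast rest on later starts and stops. Never take the value from a later dispensing.
4. Use prescriber's specialty, with Table XVII levels made mutually exclusive, in an OAC-only DOAC-versus-VKA model, in line with the first comparison in Protocol 3.7.2.2.
5. Correct the Table III cross-references in Table XV.

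The cost is SAP wording, small code changes, one OAC-only model and one sensitivity model. If the main models carry no prescriber term, some confounding control is lost. Under setting (b), with risk ratios of 1.5 (hospital) and 1.3 (general practitioner or other) against cardiologist and VKA shares of 35/25/25% against 15%, DOAC:VKA (true 1.00) becomes 0.93–0.95. The OAC-only model returns 0.99–1.01. For the unexposed contrast, the sensitivity model shows how much the choice matters.
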